- C3.2.3 Bariatric surgery: Patients will undergo the surgical procedure as recommended by their surgeon as part of their routine care at a bariatric clinic. Our preliminary data indicates that 85% of patients had a sleeve gastrectomy, 15% had a Rou-en-Y gastric bypass at the University of Michigan, and none had an adjustable gastric band. We expect a similar distribution of procedures as part of this proposed study. Patients undergoing sleeve gastrectomy and Roux-en-Y gastric bypass have similar weight loss and time to stabilization, which limits potential confounding by type of surgical procedure. ^{59, 60} Specifically, weight loss is typically 60-80 pounds at 6 mo, and 100-120 pounds at one year with stabilization at 1-1.5 yr. In contrast, adjustable gastric band procedures result in a 45-55 pound weight loss at 6 mo with stabilization at 2 yr, but this procedure is not performed at U-M. Of note, as part of their routine post-operative care, patients are supplemented with a multivitamin, sublingual B12, and calcium. Furthermore, patients have laboratory monitoring including comprehensive metabolic panel, complete blood count, B12, TSH, ferritin, and vitamin D. The prophylactic supplementation and laboratory monitoring mitigate the potential for nutritional deficiencies to lead to nerve injury and subsequent DSP. The strength of this approach is that it mirrors current practice in the bariatric surgery, a specific nutritional deficiency other than B12 deficiency is often not found. ⁶⁸
- **C3.3. Metabolic phenotyping:** These tests will aid in the appropriate description of the population, allow for adjustment of potential confounding as needed, and may provide further data in support of the metabolic factors that improve when IENFD increases over time.

Phenotypic tests will occur at baseline, 3, 12, and 24 mo, with the exception of the GTT which will only be performed at baseline. The metabolic phenotyping tests include:

 2 hr, 75 gram oral GTT with glucose and insulin levels drawn at 0, 30, 60, 90, and 120 min to allow categorization of glycemic status as well as calculation of Oral Glucose Insulin Sensitivity (OGIS).
Participants with a known diagnosis of diabetes will not complete an OGTT. Participants with a fasting glucose >126 mg/dL will not complete the test. Fasting glucose and insulin levels will be drawn at the 3, 12 and 24 month time points;

- 2. Hemoglobin A1C;

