- 14. Aerobic Assessment: All participants enrolled in the study will participate in brief graded exercise test (bike or treadmill) to determine maximal aerobic capacity (VO₂max). Participants randomized to the HIIT cohort will also complete a second VO₂max test after the training intervention to document the change in aerobic fitness. This exercise test is routinely used in clinical research projects to assess aerobic fitness in lean, obese and other clinical populations.
- 15. Dual Energy X-ray Absorptiometry: Body composition will be measured, including body fat, muscle mass and bone density using low-dose x-ray. All participants enrolled in the study will complete a DEXA scan at the beginning and end of the study.
- 16. BodPod: Subjects that exceed the weight limits of the dual energy x-ray absorptiometry may complete the BodPod as an alternative in order to determine body composition. Subjects will complete at baseline and at the end of the study.

C3.5. Visits schedule (Table 6):

| Table | 6: Study Events Sc | | | | |
|---|--------------------|--------------|------------|----------|----------------|
| Visit Number | er Visit 1 | Visit 2 | Visit 3 | Visit 4 | Visit 5 |
| Visit Descriptio | n Screening | Baseline | Outcomes | Outcomes | Outcomes |
| Time poir | nt Before baseline | Day -70 to 0 | Month 3 | Month 12 | Month 24 |
| Visit windo | w NA | 70 days | ± 14 d | ± 14 d | ± 14 d |
| Informed Consent^/study criteria | | | | | |
| Medical History Review | X | | | | |
| Stress Test | X | | | | |
| Randomized to Exercise Protocol | | X* X | | | |
| Laboratory Measures | | X | X | X | X |
| Biorepository Measures | | | | | |
| Plasma | | X | X | X | X |
| Urine | | X | | | X |
| Subcutaneous Adipose Tissue | | X | | | X |
| DNA | | X | | | |
| Skin Biopsies (IENFD) ^T | | Х | Χ | Х | X |
| Corneal confocal microscopy | | Х | Х | Х | Х |
| FDT-24-2 | | X | X | X | X |
| Retinal Imaging | | X | Χ | X | X |
| Electrophysiologic measures | | Х | | | |
| NCS | | X | | | X |
| Cardiovascular reflex tests | | | | | X |
| Cardiovascular reliex tests | | | | | |
| Clinical measures | | | | | |
| Neurologic examination | | X | | | X |
| MNSI, UENS, mTNS, SAS, DNS, DN4 | | X | X | X | X |
| McGill pain questionnaire, NRS | | Х | X | Х | Х |
| Qualitative sensory testing | | | | | |
| Neurotheisiometer | | X | X | X | X |
| | | | | | |
| Cognitive impairment | | | | | |
| NIH Toolbox | | X | | | X |
| Rey | | X | | , , | X |

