
C3.7.2 Analyses of secondary outcomes: Due to the pitfalls of multiple testing, formal statistical testing won't be performed. For analysis of repeated measures of continuous data (CCM, cardiovascular reflex tests, MNSI, UENS, mTNS, SAS, McGill Pain questionnaire, NeuroQOL, and functional assessments), the longitudinal approaches described above will be employed. Specifically, each outcome will be analyzed separately using a linear mixed effect regression model, with the treatment group as the primary exposure.

C3.7.3 Exploratory analyses: To investigate the potential modifying effects of sex, we will perform an additional analysis that includes an interaction term between the intervention groups and sex. Similarly, we will explore the differential effect of sleeve gastrectomy versus Rou-en-Y gastric bypass by including separate indicator variables for these two different surgical techniques. We will also investigate the potential weight loss independent effects of bariatric surgery by evaluating the earliest time point (3 months). In addition to other metabolic syndrome components, we will study the effect of change in insulin sensitivity as measured by OGIS on our primary outcome. Finally, we will perform an analysis of those who complete more than 80% of supervised exercise sessions to assess the effect of exercise compliance. Importantly, these analyses will be hypothesis generating for future studies.

C3.8. Power calculation: The purpose of this clinical trial is to provide the preliminary data necessary to design a multicenter clinical intervention trial. Therefore, it is not strictly amenable to formal power

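### Participants with known diabetes have no stated baseline fasting glucose or insulin, and the planned change in OGIS cannot be computed for anyone

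*Protocol*

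**What the plan says.** All references are to the Protocol.

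- **C3.3, general timing.** "Phenotypic tests will occur at baseline, 3, 12, and 24 mo, with the exception of the GTT which will only be performed at baseline".
- **C3.3, item 1, the test.** A two-hour "oral GTT with glucose and insulin levels drawn at 0, 30, 60, 90, and 120 min". These samples serve to classify glycemic status and to calculate OGIS.
- **C3.3, item 1, who does not have it.** "Participants with a known diagnosis of diabetes will not complete an OGTT"; also, "Participants with a fasting glucose >126 mg/dL will not complete the test".
- **C3.3, item 1, follow-up.** "Fasting glucose and insulin levels will be drawn at the 3, 12 and 24 month time points". Baseline is not named here.
- **C3.3, purpose.** The measures describe the population, allow adjustment for confounding, and "may provide further data in support of the metabolic factors that improve when IENFD increases over time".
- **C3.5, Table 6.** The row "Laboratory Measures | | X | X | X | X" marks baseline and every follow-up visit, without naming analytes.
- **C3.7.** OGIS is one example of the baseline variables to be compared across the four groups.
- **C3.7.3, exploratory.** "we will study the effect of change in insulin sensitivity as measured by OGIS on our primary outcome".

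**The concern.** There are two related faults in the measurement schedule.

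First, glucose and insulin appear only inside the OGTT item. The natural reading is that the time-0 OGTT sample is the baseline and that fasting samples take its place afterwards. That works for participants who have the OGTT. For those with known diabetes it yields follow-up values with nothing stated to compare them with. The gap is not random: it falls on one level of glycemic status, which is a stratification factor for randomization. A pre-treatment sample that was not taken cannot be taken later.

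Second, the one insulin-related change analysis that the Protocol names needs OGIS at two or more times. The schedule provides it at one.

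At stake is the exploratory question of whether improved insulin sensitivity goes with improved IENFD.

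**Working it through.** **Step 1. Which glucose and insulin values does the text provide?**

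| Group | Baseline glucose / insulin | Months 3, 12, 24 | Change in a fasting index | Change in OGIS |
|---|---|---|---|---|
| Has the OGTT | Time-0 sample | Fasting draw | Computable | Not computable: no follow-up OGTT |
| Fasting glucose >126 mg/dL, diabetes not previously known | Glucose implied by the rule; insulin not stated | Fasting draw | Unclear | Not computable |
| Known diabetes | None stated | Fasting draw | Not computable as stated | Not computable |

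The last column follows from C3.3 alone. OGIS comes from the OGTT, and the OGTT is done at baseline only, so the number of patients with a change in OGIS is 0 of 140. In those who skip the OGTT, baseline OGIS is missing as well.

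**Step 2. How many have no stated baseline?**

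Inputs: diabetes in the pilot bariatric cohort 25 of 71, and in the weight management cohort 30 of 125 (Table 3); planned total 140 (C3.1).

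- The Protocol's own share is reproduced: 25/71 = 35.2%.
- Scaled to the trial: 140 × 25/71 = 49.3, about 49 patients.
- Wilson 95% interval, (p + z²/2n ± z√[p(1−p)/n + z²/4n²]) / (1 + z²/n), with p = 0.3521, n = 71, z = 1.96: (0.3792 ± 0.1143)/1.0541 = 25.1% to 46.8%, or 35 to 66 of 140.
- Weight management share: 140 × 30/125 = 33.6, about 34.
- Both cohorts pooled: 55/196 = 28.1%; 140 × 55/196 = 39.3, about 39.

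Table 3 counts all diabetes, whereas only a known diagnosis triggers the first exclusion. The Protocol does not give the known share. If it is assumed to be 70% to 100%, the count runs from 0.7 × 49.3 = 34.5 (about 35; 24.6% of patients) to about 49 (35.2%).

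**Step 3. What could the scheduled samples support?**

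Fasting glucose and insulin are the only glucose and insulin samples scheduled after baseline. Any change in insulin sensitivity must therefore rest on a fasting index. C1.2.2 already describes one, HOMA-IR, calculated from fasting glucose and insulin. It could be followed over all four visits in everyone, provided that the baseline draw is secured for those who skip the OGTT.

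**The case against.** The strongest reply is that the measurement is not clearly left out. The general timing sentence puts phenotypic tests other than the GTT at baseline too, and Table 6 marks laboratory measures at baseline without excepting participants with diabetes. The >126 mg/dL rule presupposes a fasting glucose in those it screens. This stands as far as it goes: the text permits a baseline draw. It does not specify one. The fasting draws sit inside the excepted item and carry their own schedule, Table 6 lists no analytes, and the >126 mg/dL rule says nothing about insulin.

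A reader might also infer more than the Protocol supports:

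- *That every analysis of metabolic change against IENFD is lost in participants with diabetes.* It is not. HbA1c, lipids, blood pressure, BMI and waist circumference fall under the general timing rule and have baselines in all participants.
- *That the baseline is beyond recovery.* Plasma is banked at baseline, and C5 describes it as fasting. A later assay may be possible, although none is planned and C5 places studies of the stored samples outside the present proposal.
- *That a baseline fasting draw would rescue the planned analysis.* It would not. Change in OGIS fails for every patient, with or without diabetes.
- *That 49 of 140 is the expected number.* It assumes that all diabetes is already diagnosed.

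Finally, C3.7.3 labels these analyses hypothesis generating, so the consequences are limited.

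**Conclusion.** The point holds in a limited form. Participants with known diabetes have no *stated* baseline fasting glucose or insulin. That is at most about 35% of patients at the pilot share, or roughly 35 to 49 of 140 on the assumption that 70% to 100% of diabetes is already known. The size also assumes that the trial population resembles the small pilot bariatric cohort. The documents do not support the reading that the draw is definitely omitted; the passages are ambiguous and need to be reconciled.

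The second part rests on no assumption: change in OGIS, as planned, cannot be computed for anyone, because C3.3 and C3.7.3 contradict each other.

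The primary IENFD analysis does not need the fasting draw. Known diabetes already settles the glycemic stratum. The one side effect is that OGIS, named in C3.7 as a baseline variable to compare and, if different, to adjust for, will be missing in those who skip the OGTT.

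**What to change.** Make two changes together; the first is of limited use without the second.

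1. **C3.3, item 1.** State that fasting glucose and insulin are assayed at baseline, 3, 12 and 24 months in all participants, including those who do not have the OGTT. Use the fasting blood already due at baseline for the lipid panel. Name both analytes under the laboratory row of Table 6.
2. **C3.7.3.** Replace change in OGIS with change in an insulin-sensitivity index that can be computed from fasting samples at all four visits, for example HOMA-IR. Keep OGIS as a baseline descriptor in those who had the OGTT, and say so in C3.7.

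The cost is one extra glucose and insulin assay in about 35 to 49 patients, with no added visit or procedure. The scientific price is that a fasting index is a cruder measure than OGIS.

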Skin biopsy is a minimally invasive procedure, with less than 1% reporting mild adverse events such as bleeding, swelling, or erythema. It allows morphometric quantification of C-fibers in the epidermis (IENFD).77,78 Data from several clinical trials show that decreased IENFD is a robust measure of the clinical signs and symptoms of DSP^{77, 79-86} and correlates with a patient's perception of neuropathic pain.^{77, 78} Serial measurements of IENFD may be performed to assess the therapeutic efficacy of drugs^{77, 78, 87, 88} and/or lifestyle interventions³⁰ in arresting disease progression and providing pain relief, and a large normative database was recently created by an international consortium.^{77, 78, 89} Published guidelines concur that IENFD is the standard for the diagnosis of small fiber sensory neuropathy. 77, 87, 90, 91 Further support for IENFD as an early biomarker is the observation of reduced density in patients with pre-diabetes compared to those with normal glucose tolerance. 30, 83 Finally, several studies report increased IENFD in response to the rapeutic interventions that correlate with improvements in the signs and symptoms of DSP. 83-85 IENFD is also endorsed by several societies and authorities in the field as diagnostically efficient at distinguishing patients with early small fiber neuropathy from normal controls, and as a reliable and valid outcome measure to assess DSP in clinical trials. 77, 79, 87, 90, 92 In summary, IENFD is a sensitive and reliable measure of early DSP, its loss directly correlates with increasing DSP severity, is amenable to improvement with appropriate intervention, is safe and easy to perform, and to date represents the gold-standard method for evaluating morphological changes in small nerve fibers. 77, 79, 87, 90, 91 In addition, the PI has used this procedure extensively in two ongoing studies with excellent patient compliance (NS-079417 and 2P30-DK020572). Thus, IENFD was selected as the most appropriate and informative primary endpoint in the current clinical trial.

- **C3.4.2 Secondary outcomes:** Selecting the most appropriate outcome measures is critical in the design of an interventional clinical trial and essential to obtaining clinically relevant information on the true response to the intervention. Thus, we will evaluate changes from baseline to 3, 12, and 24 months in several secondary outcomes:
 - 1. IENFD at the distal leg: In addition to the IENFD measure at the proximal thigh, we will also measure

this entity at the distal leg. Previous data support that the proximal thigh measurement is more likely to show change over time after an exercise regimen in a population of patients with pre-diabetes.³⁰ However, IENFD at the distal leg will provide additional data as to the severity and length-dependence of the nerve injury. Furthermore, measurement at the distal leg may be more sensitive to change in those patients with obesity and normoglycemia, which may have milder nerve injury than those with diabetes.

- 2. Corneal confocal microscopy (CCM): While IENFD is the current gold-standard for detection of small fiber nerve injury, CCM is an innovative approach that also attempts to measure small fiber nerve injury in the cornea. This procedure is less invasive than the skin biopsy required for IENFD measurement. The benefit of including this secondary outcome measure is that we will be able to compare and contrast the diagnostic characteristics of IENFD to CCM and also determine which measure is more sensitive to change over time. This data will help determine which of these two measurements should be utilized in future intervention studies. Specifically, we will measure nerve fiber density, nerve branch density, and nerve fiber length. A recent meta-analysis revealed that all three of these parameters are reduced in those with diabetic DSP compared to those with diabetes without DSP and to healthy controls. Furthermore, studies have revealed similar diagnostic characteristics for CCM and IENFD for diabetic DSP. A cCM parameters also improve after simultaneous pancreas and kidney transplants, even when IENFD remains unchanged, indicating that CCM may be a useful early marker of nerve regeneration. Consultant [name], Associate Professor of Ophthalmology and Visual Sciences, has extensive experience utilizing CCM as an outcome measure.
- 3. Retinopathy measures:
 - a) 24-2 FDT measure of retinal ganglion function. Best corrected visual acuity will also be measured.
 - b) Retinal Imaging Retinal Fundus Photography is currently the gold standard for diagnosing and staging diabetic retinopathy.

4. Electrophysiological measures:

- a) NCS of the sural, peroneal, and tibial nerves will be obtained following the DCCT/EDIC protocol. 96, 97 Briefly, measurements will be done at the dominant limb, using temperature control. 96, 97 NCS provide a quantitative, reproducible way to evaluate for large fiber function.
- b) Measures of CAN will comprise cardiovascular reflex testing using the DCCT/EDIC protocol (R-R interval ratio during deep breathing, postural change, and Valsalva) as described. 98, 99 These tests are recommended by the Toronto Consensus Panel on Diabetic Neuropathy¹⁰⁰ as the gold-standard for CAN. We will also assess resting HR and HR variability. Consultant [name] has extensive expertise in performing and interpreting CAN outcomes in clinical trials.

Clinical DSP measures:

- a) Structured neurological examination following the DCCT/EDIC protocol^{96, 97};
- b) Michigan Neuropathy Screening Instrument (MNSI) questionnaire and examination, validated instruments to identify diabetic DSP^{103, 104};
- c) Utah Early Neuropathy Scale (UENS), a validated tool to identify small fiber predominant neuropathy such as that found in obese and pre-diabetic individuals¹⁰⁵;
- d) Modified Toronto Neuropathy Score (mTNS), a validated instrument for the detection of mild to moderate diabetic DSP¹⁰⁶; and
- e) Survey of Autonomic Symptoms (SAS), a validated measure of autonomic symptoms 107
- f) DNS-score and guidelines, a four-item validated symptom score, with high predictive value to screen for polyneuropathy.
- g) DN4 questionnaire, to assess probability of neuropathic pain.
- 6. *DSP-specific pain*: Pain will be assessed using the Short Form McGill Pain Questionnaire. This questionnaire is a reliable and validated pain questionnaire that utilizes a visual analogue scale, a 6 point rating scale of pain intensity, and a 4 point rating scale of 15 different neuropathic pain descriptors. ¹⁰⁸ Subjects will also be asked to rate their current pain on a numeric rating scale.

7. Quality of life measures:

a) We will use the NeuroQOL, a validated measure of quality of life specific to DSP,¹⁰⁹ which comprises 6 domains (pain, lost/reduced feeling, diffuse sensory-motor symptoms, restrictions in activities of daily living, disruptions in social relationships, and emotional distress) along with an overall measure of DSP impact on quality of life and general quality of life.¹⁰⁹

- b) Questionnaires that ask about the participant's mood and how weight has impacted participant's physical and emotional health. These questionnaires include the EQ-5D, IWQOL-Lite, Godin Leisure-Time Exercise, and a brief physical activity questionnaire.
- c) Demographic questionnaire will be administered to participants.

8. Functional scales:

- a) The Berg Balance Scale, measures balance in 14 separate activities of daily living (the unipedal stance portion has been shown to be particularly reflective of DSP-related mobility loss)¹¹⁰:
- b) The 8 Foot Up and Go Test, a test of functional mobility that assesses the time needed for a subject to arise from sitting position, walk 8 ft and turn 180 degrees around a cone, and return to sitting¹¹¹;
- c) The Modified Falls Efficacy Scale, assessing patient's self-reported ability to perform activities of daily living (e.g. get dressed/ undressed, walking, shopping)^{86, 112, 113} The fall survey will also ask "Have you fallen within the last year? If yes, how many falls?"

9. Qualitative sensory testing:

a) Neurothesiometer- quantitative measure of vibration threshold at both toes.

10. Cognitive impairment:

- a) NIH Toolbox Cognitive Battery A 30-minute brief computerized battery comprised of tasks covering several cognitive domains including language, attention, working memory, episodic memory, executive function, and processing speed. The NIH Toolbox Cognitive Battery is a reliable and valid instrument of cognitive function⁴⁸.
- b) The Rey Auditory Verbal Learning Test will be presented in addition to the NIH Toolbox. The Rey is presented verbally to the participant and is important as a supplement to the single visual-based short memory task in the NIH Toolbox. The computer format and national standardization of this tool will allow for comparisons to future studies. We will partner with [name] who has expertise in these cognitive assessments.
- 11. *Urine*: Urine albumin/creatinine ratio and serum creatinine measurements. Urine samples will be stored in the biorepository.
- 12. Anthropometric measurements: Body measurements at different site circumferences will be measured at each study visit including: abdomen, arm, buttocks/hips, calf, forearm, hips/thigh, mid-thigh and waist.
- 13. Orthostatic Hypotension: Blood pressure and heart rate will be assessed after patient is supine for 5 minutes, standing for 1 minute and at 3 minutes standing.
- 14. Aerobic Assessment: All participants enrolled in the study will participate in brief graded exercise test (bike or treadmill) to determine maximal aerobic capacity (VO₂max). Participants randomized to the HIIT cohort will also complete a second VO₂max test after the training intervention to document the change in aerobic fitness. This exercise test is routinely used in clinical research projects to assess aerobic fitness in lean, obese and other clinical populations.
- 15. Dual Energy X-ray Absorptiometry: Body composition will be measured, including body fat, muscle mass and bone density using low-dose x-ray. All participants enrolled in the study will complete a DEXA scan at the beginning and end of the study.
- 16. BodPod: Subjects that exceed the weight limits of the dual energy x-ray absorptiometry may complete the BodPod as an alternative in order to determine body composition. Subjects will complete at baseline and at the end of the study.

C3.5. Visits schedule (Table 6):

| Table | 6: Study Events Sc | | | | |
|---|--------------------|--------------|------------|----------|----------------|
| Visit Number | er Visit 1 | Visit 2 | Visit 3 | Visit 4 | Visit 5 |
| Visit Descriptio | n Screening | Baseline | Outcomes | Outcomes | Outcomes |
| Time poir | nt Before baseline | Day -70 to 0 | Month 3 | Month 12 | Month 24 |
| Visit windo | w NA | 70 days | ± 14 d | ± 14 d | ± 14 d |
| Informed Consent^/study criteria | | | | | |
| Medical History Review | X | | | | |
| Stress Test | X | | | | |
| Randomized to Exercise Protocol | | X* X | | | |
| Laboratory Measures | | X | X | X | X |
| Biorepository Measures | | | | | |
| Plasma | | X | X | X | X |
| Urine | | X | | | X |
| Subcutaneous Adipose Tissue | | X | | | X |
| DNA | | X | | | |
| Skin Biopsies (IENFD) ^T | | Х | Χ | Х | X |
| Corneal confocal microscopy | | Х | Х | Х | Х |
| FDT-24-2 | | X | X | X | X |
| Retinal Imaging | | X | Χ | X | X |
| Electrophysiologic measures | | Х | | | |
| NCS | | X | | | X |
| Cardiovascular reflex tests | | | | | X |
| Cardiovascular reliex tests | | | | | |
| Clinical measures | | | | | |
| Neurologic examination | | X | | | X |
| MNSI, UENS, mTNS, SAS, DNS, DN4 | | X | X | X | X |
| McGill pain questionnaire, NRS | | Х | X | Х | Х |
| Qualitative sensory testing | | | | | |
| Neurotheisiometer | | X | X | X | X |
| | | | | | |
| Cognitive impairment | | | | | |
| NIH Toolbox | | X | | | X |
| Rey | | X | | , , | X |
| Anthropometric measures^ | | X | X | X | X |
| Orthostatic Hypotension Assessment [^] | | Х | X | X | Х |
| Quality of Life measures: | | | | | |
| NeuroQol | | X | X | X | X |
| Questionnaires | | X | Х | Х | X |
| Demographics | | X | | | |
| Functional Assessments | | | , . | , . | |
| Berg Balance Scale [^] | | X | X | X | X |
| 8-foot Get Up and Go Test^ | | X | X | X | X |
| Modified Falls Efficacy Scale | | Х | X | Х | Х |
| Aerobic Assessment | | | | | |
| VO2 max | X | | | | X ⁺ |
| | | | | | |
| Dual Energy X-ray Absorptiometry | | | | | |
| Duai Lineigy A-iay Absorptionietry | | X | | | X |

^{*}Randomization to exercise protocol to occur after baseline visit

Data collected for clinical purposes as part of the Adult Bariatric Surgery Program will be reviewed as part of this study and included in the study records.

- **C3.6. Timeline and milestones:** The planned study duration is 5 yr, with 2 yr of subject accrual, 2 yr of subject follow-up, plus 1 yr for analysis and results presentation.
- **C3.7. Statistical analysis:** The four treatment groups (HIIT/no surgery, HIIT/surgery, routine exercise/no surgery, routine exercise/surgery) will be compared with respect to demographic and baseline variables (e.g., age, sex, glycemic status, OGIS, BMI, etc.). If a significant difference is found in any variable, the models described below will be fitted after adjusting for these variables.
- C3.7.1 Analysis of primary outcome: The primary outcome is IENFD at the proximal thigh, measured at baseline, 3, 12, and 24 mo. Exploratory analysis will be performed to assess the need for any transformation

^{*}Only participants randomized to the HIIT will complete a second time

 $^{^{\}mathsf{T}}$ Participants can consent to have skin biopsy added to biorepository

[^]Participants may complete the consent and outcomes virtually prior to the upcoming visit to decrease in-person interaction due to Covid-19. If the outcome cannot be completed successfully it with be completed during the visit.

on the primary outcome variable. The primary exposure variables are HIIT: yes/no (Aim 1), and bariatric surgery: yes/no (Aim 2). We will adjust for demographic, clinical, and baseline characteristics as covariates in the model. In addition to the main effects of HIIT exercise program and bariatric surgery, we will also examine selected interactions based on *a priori* considerations. In particular, we will focus on the interaction between HIIT and bariatric surgery to assess if the effect of HIIT exercise on IENFD is modified by bariatric surgery. Linear mixed effects regression modeling will be used to determine the relationship between the primary exposure variables and IENFD over time. Longitudinal data analysis approaches such as this offer enhanced statistical power, as subjects are able to serve as their own reference. Furthermore, linear mixed effects regression offers a flexible framework to handle missing data such as due to attrition. Let Y_{it} denote the IENFD of the *i*th patient at the *t*th time point. Then Y_{it} can be modeled using the random intercept model.¹¹⁴ The random intercept model can be viewed as arising from a two-stage model as follows:

Stage 1: subject-specific trajectory: $Y_{it} = \mu_{0i} + \lambda' Z_i + \underline{\theta' X}_{it} + \underline{e}_{it}$

Stage 2: between-subjects: $\mu_{0i} = \beta_{00} + \beta_{0i}$

Combining the two stages, we can write $Y_{it} = \beta_{00} + \beta_{0i} + \theta' X_{it} + e_{it}$

where β_{00} is the population-averaged intercept, Z_i is the matrix of main effects and interaction corresponding to HIIT exercise and bariatric surgery, \underline{X}_{it} is the matrix of fixed covariates (demographic and baseline characteristics), λ and θ are the vectors of corresponding fixed effects parameters, β_{0i} is the subject-specific random (intercept) effect capturing heterogeneity across subjects due to unmeasured confounders, and en is the random error characterizing variation due to sources like within-subject fluctuations and measurement error. The random effect β_{0i} is assumed to follow a normal distribution with mean zero and variance σ^2_{sub} , and the eit's are assumed to be distributed normally with mean **0** and variance covariance matrix R (non-diagonal). Furthermore, we also assume that θ_{0i} and e_{it} are independent. Maximum likelihood method will be used to estimate the model parameters. We will use Akaike Information Criterion (AIC) and Schwarz Bayesian Information Criterion (BIC) to guide the selection of the covariance structure. Inference for λ (which is of primary interest) will be based on Wald tests. We will use PROC MIXED in SAS to fit the above model. To explore potential non-linear or threshold effect of treatment exposure on IENFD we will use a nonparametric regression model fitted using the framework of generalized additive models (GAM). 115 Given the exploratory nature of the research proposed here, the GAM models will allow us the flexibility to include a smooth functional term instead of restricting to a linear relationship. The smoothing term is fitted by using penalized regression splines or locally smoothed loess curves, with the degree of smoothness chosen in a data-adaptive way, using cross-validation techniques. We will use the gam function in the mgcv package available in the R software to fit these non-parametric regression models. We will perform sensitivity analyses to assess how subjects who withdrew affect conclusions of the analysis. An intent-to-treat analysis set (including subjects who are randomized, treated, and have a baseline IENFD) will be used to assess treatment effects, with multiple imputation methods¹¹⁶ employed to impute outcomes for subjects with missing post-baseline data. Depending on the extent and pattern of missingness, other simpler sensitivity analyses may be used: e.g., subjects completing the study (completers) may be analyzed using a repeated measures analysis of variance model. The model will include the same covariates that are included in the primary analysis.

C3.7.2 Analyses of secondary outcomes: Due to the pitfalls of multiple testing, formal statistical testing won't be performed. For analysis of repeated measures of continuous data (CCM, cardiovascular reflex tests, MNSI, UENS, mTNS, SAS, McGill Pain questionnaire, NeuroQOL, and functional assessments), the longitudinal approaches described above will be employed. Specifically, each outcome will be analyzed separately using a linear mixed effect regression model, with the treatment group as the primary exposure.

C3.7.3 Exploratory analyses: To investigate the potential modifying effects of sex, we will perform an additional analysis that includes an interaction term between the intervention groups and sex. Similarly, we will explore the differential effect of sleeve gastrectomy versus Rou-en-Y gastric bypass by including separate indicator variables for these two different surgical techniques. We will also investigate the potential weight loss independent effects of bariatric surgery by evaluating the earliest time point (3 months). In addition to other metabolic syndrome components, we will study the effect of change in insulin sensitivity as measured by OGIS on our primary outcome. Finally, we will perform an analysis of those who complete more than 80% of supervised exercise sessions to assess the effect of exercise compliance. Importantly, these analyses will be hypothesis generating for future studies.

C3.8. Power calculation: The purpose of this clinical trial is to provide the preliminary data necessary to design a multicenter clinical intervention trial. Therefore, it is not strictly amenable to formal power

considerations. However, there are two assumptions necessary to justify the multicenter trial. The first is that HIIT will cause an increase in IENFD (re-innervation) and the second is that the natural progression of DSP is loss of nerve fibers over time. The primary outcome is an assessment of IENFD at the proximal thigh over 4 time points spanning 24 mo in the four trial arms. To estimate the likely effect sizes of the four interventions, we will rely on previous well-conducted studies, including our ongoing NIH K23 project. For the routine exercise/no surgery group, we estimate that the IENFD will decrease similar to that observed for those with pre-diabetes and DSP. Over 26.7 mo, IENFD at the proximal thigh decreased from 19±5 to 13±4. Given that our population includes patients with normoglycemia, we expect a decline of at least 3 fibers/mm over the 2 yr of our study. For the HIIT/no surgery group, we estimate that the IENFD will increase by 1.4±2.3 fibers/mm based on a study of the effect of exercise by Smith et al.³⁰ They saw this effect after 1 yr, but we will conservatively estimate that the effect will plateau after the initial yr after the intervention. For routine exercise/surgery group, we estimate that the IENFD will increase by 0.2±7.0 based on our preliminary data on patients undergoing diet-induced weight loss for 2 yr. For the HIIT/surgery group, we estimate that the effect will be additive compared to the two separate interventions. With our expected sample size of 30 patients (allowing for ~15% attrition) in each of the four treatment groups, we will have at least 80% power to detect effect sizes between 0.9 and 1.7 as statistically significant based on a two-sided test with alpha=0.05.

- **C3.9. Data collection and management:** Data report forms will be filled out during each visit, verified, and entered into RedCap. Validation reports will be run, and checked for omissions, improbable values, and data consistency. Distributions of continuous measures will be assessed for symmetry and transformations will be applied as needed. Co-investigator [name], Professor of Biostatistics, [name], graduate student, and [name] will have data access for monitoring and verification.
- **C3.10. Recruitment and retention plan:** [name] has experience recruiting obese participants for two epidemiologic cohorts, his NIH K23 and 2P30-DK020572 grants, that provided the preliminary data for the proposed study. He works closely with [name] (project coordinator) and [name] (research coordinator) on these projects. Both coordinators have successfully recruited subjects for these studies, developed strategies for retention, and can perform the outcomes measures required for this proposal.
- C3.10.1 Recruitment strategies: Patients will be recruited from a bariatric surgery clinic. Recruitment for the study begins at the informational session, where flyers are passed out providing information about the study as well as contact information for the study team. Patients are then recruited one-on-one during their bariatric surgery clinic visits. Patients meet individually with the study coordinator to discuss the study, answer questions, and begin the scheduling process. Patients are then followed as they complete the requirements prior to surgery, and are emailed at different time points to check for interest in participation. The final face-to face interaction for recruitment is during the required nutrition information session. Patients will be consented once they have made a decision whether or not to have surgery. This multi-step approach to recruitment has been effective for our ongoing bariatric surgery study. Compared with the start of the ongoing project, we have added multiple points of face-to-face contact and added a mixed media presentation, which will only increase the feasibility of the current proposal.
- C3.10.2 Retention strategies: Patients will be emailed and/or called to schedule their 3, 12, and 24 mo visits approximately 2-3 mo prior to the date. We will also call patients monthly to address any concerns and discuss compliance. This limits the amount of time that the study team is not in contact with the participant, helping to increase patient retention. Patients are mailed out a reminder post-card just prior to the 1-yr and 2-yr mark, thanking them for their participation and reminding them that we will be in contact with them. This patient population has proven to be committed and motivated to participate in our current study, with 94% retention.
